9.2.4 SAEs (Including Deaths) and Adverse Events Leading to Study Drug Discontinuation

SAEs (including deaths) and AEs leading to study drug discontinuation will be summarized by SOC and PT and in listing format. Listing of all adverse events for subjects experiencing death will be produced.

9.2.5 Adverse Events of Special Interest

Treatment-emergent adverse events of special interest will be summarized by SOC and PT and by maximum severity and will be based on standardized MedDRA queries (SMQs) or company MedDRA queries (CMQs). Infusion reactions are considered to be adverse events of special interest for elezanumab and will be display by each category provided in [Appendix B](#).

Detailed information about the search criteria is provided in [Appendix B](#).

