AbbVie will provide study drug as liquid in a vial that requires sterile preparation. The start of the first infusion of study drug must occur as soon as possible but no later than 6 hours after randomization. The study drug can be administered without regard to food consumption and infusion time is 90 to 120 minutes. The start and stop time of each study drug infusion will be recorded to the nearest minute. Please refer to the pharmacy manual for detailed instructions.

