Reasonable Possibility	After consideration of factors including timing of the event, biologic plausibility, clinical judgment, and potential alternative causes, there is sufficient evidence (information) to suggest a causal relationship.
No Reasonable Possibility	After consideration of factors including timing of the event, biologic plausibility, clinical judgment, and potential alternative causes, there is insufficient evidence (information) to suggest a causal relationship.

Adverse events will be monitored throughout the study to identify any of special interest that may indicate a trend or risk to subjects.

Adverse Events of Special Interest

The following AESIs will be monitored during the study (see Operations Manual [[Appendix F](#)] for more information):

- Infusion reactions

Pregnancy

While not an AE, pregnancy in a study subject must be reported to AbbVie within 24 hours after the site becomes aware of the pregnancy. Subjects who become pregnant during the study must be discontinued (Section 5.5). If a pregnancy occurs in a study subject, information regarding the pregnancy and the outcome will be collected.

The pregnancy outcome of an elective or spontaneous abortion, stillbirth or congenital anomaly is considered a SAE and must be reported to AbbVie within 24 hours after the site becomes aware of the event.

Safety Monitoring

An external DMC composed of persons independent of AbbVie and with relevant expertise in stroke and clinical trial safety monitoring will review unblinded data from the ongoing study. The primary responsibility of the DMC will be to protect the safety of the subjects participating in this study.

A separate DMC Charter will be prepared outside of the protocol and will describe the roles and responsibilities of the DMC members, frequency of data reviews, relevant data to be assessed, and expectations for blinded communications.

[figure not shown]

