9.2.1 Treatment-Emergent Adverse Events

Treatment-emergent AEs are defined as any AE with the onset that is on or after the first dose date. Events where the onset date is the same as the study drug start date are assumed to be treatment-emergent. All treatment-emergent AEs will be summarized overall, as well as by primary MedDRA SOC and Preferred Term. The SOCs will be presented in alphabetical order, and the PTs will be presented in alphabetical order within each SOC.

The number and percentage of subjects experiencing treatment-emergent AEs will be summarized.

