Appendix B. Definition of Adverse Events of Special Interest and Recurrent Stroke Events

Adverse Events of Special Interest (AESI) and recurrent stroke events will be identified using the following search criteria:

Area of Safety Interest	Search Criteria		
	Type	Name	Code
Infusion reactions	CMQ	Drug-induced rash	10000050
	SMQ	Hypersensitivity	20000214
	SMQ	Angiodema	20000024
	SMQ	Anaphylactic reaction	20000021
	CMQ	Injection site reaction	10000091
Recurrent stroke events	Type	Name	Code
	SMQ	Embolic and thrombotic events	20000081
	SMQ	Embolic and thrombotic events, arterial	20000082
	SMQ	Embolic and thrombotic events, venous	20000084
	SMQ	Embolic and thrombotic events, vessel type unspecified and mixed arterial and venous	20000083

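### The SAP reports 'infusion reactions', the only AESI, from term searches with no link to infusion timing, so matching events up to 39 weeks after the last dose are counted

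*SAP*

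**What the plan says.** Protocol 6.1 introduces its list with "The following AESIs will be monitored during the study". The list has one entry, infusion reactions, and refers to the Operations Manual for more information.

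SAP 9.2.5 repeats this: "Infusion reactions are considered to be adverse events of special interest for elezanumab". It displays them by each Appendix B category. The summaries are by SOC and preferred term and by maximum severity.

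Appendix B opens: "Adverse Events of Special Interest (AESI) and recurrent stroke events will be identified using the following search criteria". For infusion reactions it lists five MedDRA queries, each with a type, a name and a code: drug-induced rash, hypersensitivity, angioedema, anaphylactic reaction and injection site reaction. It has no entry for onset time.

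The only time rule that applies is treatment-emergence in SAP 9.2.1, which requires onset on or after the first dose date and sets no end. Protocol 6.1 collects adverse events from study drug administration until 39 weeks after the drug is stopped.

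On infusion timing, Protocol 5.7 says: "The start and stop time of each study drug infusion will be recorded to the nearest minute". The AESI definition does not use these times.

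**The concern.** The label claims a relation to the infusion that the definition does not test. Followed exactly, the plan would report a rash that begins months after the last infusion as an infusion reaction if its term falls in one of the five queries, whatever its cause.

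Two things are at stake. First, the reported percentage would be read as infusion tolerability, but it is the frequency of hypersensitivity-type events over well over a year. Second, if elezanumab does cause reactions around infusions, they are mixed with background events expected in both arms. With about 60 subjects per arm, a small excess then becomes harder to see.

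**Working it through.** **Inputs from the documents**
- Dosing every 4 weeks through Week 48, 13 doses (Protocol 4.1, SAP 2.2).
- Adverse event collection to 39 weeks after the drug is stopped (Protocol 6.1). SAP 7.3 gives 39 weeks as 273 days.
- About 120 subjects randomized 1:1, so about 60 per arm (Protocol 5.8).

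**Reproducing the plan's figures.** Doses at Weeks 0, 4, ..., 48: 48/4 + 1 = 13, as stated. 39 × 7 = 273 days, as stated.

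**Length of the AESI window for a subject given all doses.** 48 + 39 = 87 weeks; 336 + 273 = 609 days.

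**Share of that window near an infusion.** Share = 13 × window length / 609. The window lengths are assumptions.

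| Window per infusion | Days covered | Share of 609 days |
|---|---|---|
| 2 hours (the longest stated infusion time) | 1.1 | 0.2% |
| 24 hours | 13 | 2.1% |
| 48 hours | 26 | 4.3% |
| 72 hours | 39 | 6.4% |

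Even at 72 hours, more than 93% of the time in which a matching event counts lies outside the window. For a subject who stops after one dose but stays in follow-up, a 24-hour window covers 1/273 = 0.4%.

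**Background events counted.** The documents give no background rate, so a range is shown. Subjects per arm with at least one event = 60 × (1 − exp(−rate × days/365.25)), with full follow-up and a constant rate.

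| Assumed rate per subject-year | Untimed, 609 days | 24-hour windows, 13 days |
|---|---|---|
| 2% | 2.0 | 0.04 |
| 5% | 4.8 | 0.11 |
| 10% | 9.2 | 0.21 |
| 20% | 17.0 | 0.43 |

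**Effect on a real signal (illustration, all rates assumed).** Suppose 10% of each arm has a background event over the full window, and true infusion reactions occur in 5% on elezanumab and 0% on placebo.
- Untimed: elezanumab 1 − 0.90 × 0.95 = 14.5%, placebo 10%. Ratio 1.45, difference 4.5 points. Standard error = √(0.145 × 0.855/60 + 0.10 × 0.90/60) = 6.0 points.
- Timed, 24 hours: background 10% × 0.0213 = 0.21%. Elezanumab 1 − 0.9979 × 0.95 = 5.2%, placebo 0.2%. Difference 5.0 points. Standard error = √(0.052 × 0.948/60 + 0.0021 × 0.9979/60) = 2.9 points.

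The absolute difference barely moves. Its standard error roughly doubles when timing is ignored, and the ratio falls to 1.45.

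**The case against.** **Attribution is already planned.** SAP 9.2.2 gives an AESI overview for each query, with rows for events the investigator considers related and for serious related events. Protocol 6.1 has the investigator weigh timing and alternative causes. A rash from another drug should mostly drop out of the related rows. This stands and reduces the harm. It remains a causality judgement, not a timing rule, and 9.2.5 still labels every match an infusion reaction.

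**The result is not one pooled number.** Display by query, SOC, preferred term and severity shows which terms drive the count. It does not show when they occurred relative to an infusion.

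**Infusion tolerability is partly covered elsewhere.** SAP 9.4 compares pre- and post-infusion vital signs, and Appendix C has post-infusion blood pressure criteria. This is true, but it does not replace timed adverse events.

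**The comparison is fair between arms.** Both arms receive infusions and the same search, safety is not tested formally (Protocol 7.4), and the risk difference is nearly unchanged. This stands: no directional bias is shown.

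**A definition may exist elsewhere.** The Operations Manual, to which Protocol 6.1 refers, is not among the documents and may contain a timed definition. SAP 9.2.5 and Appendix B, which define the analysis, import none.

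**Two stronger readings are tempting.** First, SAP 9.2.1 says "Events where the onset date is the same as the study drug start date are assumed to be treatment-emergent", and a reader might infer that allergic reactions to thrombolysis hours before the first infusion would be counted. Protocol 6.1 collects only study procedure-related events before dosing, and thrombolysis and EVT are standard of care, so such reactions should largely not be collected. Second, a reader might take infusion reactions to be the trial's only prespecified safety signal. It is the only AESI, but the SAP also prespecifies recurrent stroke events (9.2.3), hepatotoxicity criteria (9.3) and hemorrhagic transformation (9.5.3).

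**Conclusion.** The point holds as one of labelling and precision. The AESI called infusion reactions has no link to infusion timing, and its window runs up to 87 weeks for a subject given all 13 doses. Under an assumed 24-hour window, 596 of 609 days (about 98%) lie outside it. That is a share of time. It becomes a share of background events only if they are evenly spread, and it assumes full dosing and follow-up; observation is shorter for subjects who die or withdraw.

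How many unrelated events would be counted cannot be derived from the documents. The range of about 2 to 17 subjects per arm rests on assumed rates of 2% to 20% per subject-year. The consequences are a rate that does not describe infusion tolerability, a diluted ratio and a less precise difference. The change is worth making because it is cheap, but it does not threaten the safety comparison as a whole.

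**What to change.** In SAP 9.2.5 and Appendix B:

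1. Add an infusion-reaction row limited to matching events with onset at or after the start of an infusion and within a prespecified time of its end, using the recorded infusion times. Twenty-four hours is an example. The sponsor should justify the length and align it with any definition in the Operations Manual.
2. State a fallback in case clock times of adverse event onset are not collected, which the documents do not settle: onset date equal to the infusion date or the next day. This covers up to 26 of 609 days (4.3%). It cannot separate onset before an infusion from onset after it on the same date, and the SAP should say so.
3. Keep the existing untimed search, relabelled 'hypersensitivity-type events, any time', with its present breakdowns and relatedness rows.

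The cost is a short SAP addition, a date or time filter and one more row. Under the date fallback it needs no clock times for adverse events. The small downside is that delayed reactions fall outside the timed row, but they stay visible in the untimed one.

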9.3 Analysis of Laboratory Data

Data collected from central and local laboratories, including additional laboratory testing due to an SAE, will be used in all analyses, except for Baseline where SAE-related laboratory assessments on or before the first dose of study drug will be excluded. The clinical laboratory tests defined in the protocol operations manual (e.g., hematology and clinical chemistry) will be summarized.

Each laboratory variable will be summarized for all time points (starting with Baseline) as well as minimum value, maximum value, and final value, with the number of non-missing observations, mean and standard deviation, median, minimum, and maximum.

Mean change from baseline to each applicable post-baseline visit will be summarized for PT, aPTT, total cholesterol, and triglycerides, with the number of observations, baseline mean, and visit mean. The mean change from baseline, standard error, and 95% confidence interval will be presented within each treatment group and between treatment group difference (active vs. placebo) based on an ANCOVA with baseline as a covariate and treatment as a main effect.

Changes in laboratory parameters will be tabulated using shift tables categorized as low, normal, or high based on the normal ranges of the laboratory used for each sample. A shift table from baseline to minimum and maximum value (based on normal range), will be created. A similar shift table will be provided to summarize shifts from baseline to the final post-baseline value. Listing of subjects with lab abnormalities meeting CTC Criteria Grade 3 or 4 will be provided.

Laboratory abnormalities will be evaluated based on Potentially Clinically Significant (PCS) criteria ([Appendix C](#)). For each laboratory PCS criterion, the number and percentage of subjects who have a laboratory value meeting the criteria will be summarized. Listings will be provided to summarize subject-level laboratory data for subjects meeting PCS criteria.

The following criteria will be used to assess for potential hepatotoxicity. The number and percentage of subjects meeting each of the following criteria will be summarized by treatment group, and a listing of ALT, AST, TBL, and alkaline phosphatase at each time for all subjects that met any of the criteria below at any time will be produced.

- ALT $\geq 3 \times$ ULN, $\geq 5 \times$ ULN, $\geq 10 \times$ ULN, $\geq 20 \times$ ULN
- AST $\geq 3 \times$ ULN, $\geq 5 \times$ ULN, $\geq 10 \times$ ULN, $\geq 20 \times$ ULN
- TBL $\geq 1.5 \times$ ULN, $\geq 2 \times$ ULN
- ALT and/or AST $\geq 3 \times$ ULN and TBL $\geq 1.5 \times$ ULN
- ALT and/or AST $\geq 3 \times$ ULN and TBL $\geq 2 \times$ ULN
- ALT $\geq 3 \times$ ULN and TBL $\geq 1.5 \times$ ULN
- ALT $\geq 3 \times$ ULN and TBL $\geq 2 \times$ ULN

- Alkaline phosphatase $\geq 1.5 \times \text{ULN}$

A listing of possible Hy's Law cases, defined as those who meet all of the following conditions simultaneously, will be provided: ALT $\geq 3 \times \text{ULN}$ or AST $\geq 3 \times \text{ULN}$. that is associated with an increase in bilirubin $\geq 2 \times \text{ULN}$ and alkaline phosphatase $< 2 \times \text{ULN}$.

9.4 Analysis of Vital Signs and Weight

Vital sign measurements of systolic and diastolic blood pressure, pulse rate, and body temperature, as well as weight will be summarized.

Each vital sign variable will be summarized for all time points (starting with Baseline) for the pre-infusion value with the number of non-missing observations, mean and standard deviation, median, minimum and maximum.

Mean change from baseline to each applicable post-baseline visit based on the pre-infusion value will be summarized for each vital sign variable, with the number of observations, baseline mean, and visit mean. The change from baseline mean, standard error, and 95% confidence interval will be presented within each treatment group and between treatment group difference (elezanumab vs. placebo) based on an ANCOVA with baseline as a covariate and treatment as a main effect.

The pre-infusion and post-infusion means will be calculated for each infusion visit (time point) for subjects who have both values. The change from pre-infusion to post-infusion mean, standard error, and 95% confidence interval will be presented for within each treatment group and between treatment groups (elezanumab vs. placebo) based on an ANCOVA with baseline as a covariate and treatment as a main effect.

Vital sign variables will be evaluated based on potentially clinically significant (PCS) criteria ([Appendix C](#)). For each vital sign PCS criterion, the number and percentage of subjects who have a vital sign value meeting the criteria will be summarized. Listings will be provided to summarize subject-level vital sign data for subjects meeting PCS criteria.

9.5 Other Safety Analyses

9.5.1 Analysis of ECG Parameters

The proportion of subjects with Normal, Abnormal - not clinically significant and Abnormal - clinically significant electrocardiogram (ECG) readings will be summarized at each visit ECG is performed for each treatment group and all subjects overall. Listings will be provided to summarize subject-level ECG data for subjects meeting PCS criteria.

9.5.2 Analysis of Columbia-Suicide Severity Rating Scale (C-SSRS)

The Columbia-Suicide Severity Rating Scale (C-SSRS) is a systematically administered instrument developed to track suicidal adverse events across a treatment study. At Day 2-4 the C-SSRS will be administered to collect prior to study entry. At all other visits, the C-SSRS will collect experience since the last visit. Affirmative responses on the C-SSRS will be summarized for the initial screening and each subsequent visit for each treatment group and all subjects overall.

Each summary will include the number and percentage of subjects with one or more affirmative responses to each of the 5 suicidal ideation questions, each of the 6 suicidal behavior questions, any of the 5 suicidal ideation questions, any of the 6 suicidal behavior questions, any suicidal ideation or behavior question, and the self-injurious behavior without suicidal intent. A listing will also be prepared that includes all subjects with 1 or more affirmative responses.

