3.4 Safety Endpoints

Safety evaluations include AE monitoring, adverse events of special interest (AESI) monitoring, physical examinations, neurological examinations, vital sign measurements, clinically significant magnetic resonance imaging (MRI) abnormalities, electrocardiogram (ECG) variables, Columbia-Suicide Severity Rating Scale (C-SSRS) assessments, and clinical laboratory testing (hematology, chemistry, and urinalysis) as measures of safety and tolerability for the entire study duration.

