An important medical event that may not be immediately life-threatening or result in death or hospitalization, but based on medical judgment may jeopardize the subject and may require medical or surgical intervention to prevent any of the outcomes listed above (i.e., death of subject, life threatening, hospitalization, prolongation of hospitalization, congenital anomaly, or persistent or significant disability/incapacity). Additionally, any elective or spontaneous abortion or stillbirth is considered an important medical event.

All AEs reported from the time of study drug administration until 39 weeks (5 half-lives) after discontinuation of study drug administration will be collected, whether solicited or spontaneously reported by the subject. In addition, study procedure-related serious and nonserious AEs will be collected from the time the subject signs the study-specific informed consent.

The following definitions will be used for Serious Adverse Reactions (SAR) and Suspected Unexpected Serious Adverse Reactions (SUSAR):

SAR	Defined as all noxious and unintended responses to an Investigational Medicinal Product (IMP) related to any dose administered that result in an SAE as defined above
SUSAR	Refers to individual SAE case reports from clinical trials where a causal relationship between the SAE and the IMP was suspected by either the sponsor or the investigator, is unexpected (not listed in the applicable Reference Safety Information), and meets one of the above serious criteria.

AbbVie will be responsible for SUSAR reporting for the IMP in accordance with global and local requirements.

Adverse events will be monitored throughout the study to identify any of special interest that may indicate a trend or risk to subjects.

Adverse Event Severity and Relationship to Study Drug

The investigators will rate the severity of each AE as mild, moderate, or severe.

The investigator will use the following definitions to rate the severity of each AE:

Mild	The adverse event is transient and easily tolerated by the subject.
Moderate	The adverse event causes the subject discomfort and interrupts the subject's usual activities.
Severe	The adverse event causes considerable interference with the subject's usual activities and may be incapacitating or life threatening.

The investigator will use the following definitions to assess the relationship of the AE to the use of study drug:

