2.2 Study Design Overview

[figure not shown]
This is a 52-week, Phase 2a, randomized, double-blind, parallel-group, placebo-controlled, multicenter proof-of concept study to evaluate the safety and efficacy of elezanumab in subjects with acute ischemic stroke.

Administration of blinded study drug must be initiated as soon as possible but no later than 6 hours after randomization and done every 4 weeks thereafter through Week 48 for a total of 13 doses. The final double-blind Treatment Period study visit will be at Week 52. Subjects will have 2 post-treatment follow-up visits at 12 and 24 weeks after last dose of study drug, and a final follow-up phone call 39 weeks (~5 half-lives) after last dose of study drug.

Final efficacy analyses will be performed after the last subject completes the Week 52 visit and after an interim database lock. Final safety analyses will be performed following completion of the post-treatment period and final database lock.

The schematic of the study is shown in [Figure 1](#).

Figure 1. Study Schematic

EVT endovascular therapy; hr(s) hour(s); IV intravenous; LKN last known normal; tPA tissue plasminogen activator; Wk week

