3.5 Other Endpoints

Brain MRI scans will be obtained for all subjects at Baseline (collected between 2-4 days after randomization) and follow-ups (Week 4 and Week 52). Images will be analyzed to assess infarct (ischemic core and penumbra) and presence of microstructural damage related to myelin loss and axonal destruction.

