8.3.3 Primary Efficacy Analysis

The primary efficacy analysis will be based on the monthly-adjusted area under the curve (AUC) derived from an MMRM. The dependent variable is the NIHSS total score during the Treatment Period. The model will include the stratification factors of tPA use (Y/N), EVT use (Y/N), time since last known normal (≤ 12 hours, > 12 hours based on time between last known normal and study drug initiation), main effects of treatment group and visit, and the treatment-by-visit interaction. The REPEATED statement will be used for visit with blocks in the covariance matrix identified by subject nested within treatment group. The unstructured covariance structure will be used to estimate the within subject variance-covariance; if the model does not converge with this variance-covariance structure, then compound symmetry will be used.

The monthly-adjusted AUC of NIHSS total score for each treatment group will be obtained using the trapezoidal method where i = treatment group (placebo, elezanumab) and j = visit during the Treatment Period {Day 1, Day 2-4, Week 4, Week 8, Week 12, Week 24, Week 36, Week 52}:

$$AUC_i = \frac{1}{13} \sum_{j=Stabil.(Day 2-4)}^{Week 52} \frac{(Week Number_j - Week Number_{j-1})}{4} \frac{1}{2} (LS Mean_{i,j} + LS Mean_{i,j-1})$$

The AUC for each treatment group, as well as the difference in AUCs (placebo minus elezanumab) and their respective standard errors and confidence intervals will be presented.

The posterior probability that the difference in AUCs being greater than 0.6 based on the observed data will be presented.

The attributes of the estimand corresponding to the primary efficacy objective are summarized in [Table 1](#).

Table 1. Summary of the Estimand Attributes Corresponding to the Primary Efficacy Objective

Estimand Label	Attributes of the Estimand					Statistical Summary
	Treatment	Endpoint	Population	Handling of Intercurrent Events		
NIHSS total score AUC	Elezanumab 1800 mg or placebo IV Q4W (13 doses)	NIHSS total score at each visit	FAS	Missing data due to intercurrent events (e.g., premature discontinuation of study drug, lost to follow-up, death, COVID-19) will be handled using MMRM with MAR assumption	Difference in monthly-adjusted AUC between treatment groups	

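### As worded, SAP 9.5.2 leaves the days from first dose to the Day 2-4 visit outside every C-SSRS recall window, so events then are missing from, or misplaced in, the C-SSRS tables

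*SAP*

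**What the plan says.** SAP 9.5.2 sets two recall rules. For the first administration it describes: "At Day 2-4 the C-SSRS will be administered to collect prior to study entry". For the rest: "At all other visits, the C-SSRS will collect experience since the last visit".

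The reporting rule follows: "Affirmative responses on the C-SSRS will be summarized for the initial screening and each subsequent visit". Subjects with any affirmative response are also listed.

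On timing, SAP 2.2 states: "Administration of blinded study drug must be initiated as soon as possible but no later than 6 hours after randomization". The visit set in SAP 8.3.3, given for the NIHSS, runs "Day 1, Day 2-4, Week 4, Week 8, Week 12, Week 24, Week 36, Week 52". SAP 3.5 describes the baseline MRI as "collected between 2-4 days after randomization", which is the only explicit anchor the SAP gives for a window of this kind.

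Protocol 3.4 lists the C-SSRS among several safety evaluations that serve "as measures of safety and tolerability for the entire study duration". Protocol 6.1 sets adverse event collection separately: "All AEs reported from the time of study drug administration until 39 weeks (5 half-lives) after discontinuation of study drug administration will be collected".

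**The concern.** The first C-SSRS is given after the first infusion but asks about the time before the study. The next one looks back only as far as the Day 2-4 visit. Consider a subject assessed on Day 4 whose suicidal ideation began on Day 2. It began after study entry, so it is outside the first form. It began before the last visit, so it is outside the second.

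The labelling adds a second difficulty. The summary starts with a screening column, but SAP 9.5.2 describes no screening C-SSRS; the first administration it mentions is at Day 2-4. If the subject volunteers the Day 2 ideation on that form, the SAP gives no rule for separating it from lifetime or recent history.

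At stake is the C-SSRS record of the days just after the first infusion and the acute stroke. The tables would understate on-treatment ideation or behaviour there, either by omission or by placing it with pre-study history.

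**Working it through.** The SAP gives no figure to reproduce, so the check is a timeline followed by simple arithmetic.

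**Recall windows against the dosing timeline**

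| Step | Source | What it covers |
|---|---|---|
| First dose | SAP 2.2; Protocol 4.1 and 5.7 | Starts within 6 hours of randomization, so before the Day 2-4 visit |
| C-SSRS at Day 2-4 | SAP 9.5.2 | Up to study entry |
| Next C-SSRS | SAP 9.5.2 | From the previous visit (Day 2-4, on the plain reading) onward |
| First dose to Day 2-4 visit | none | No C-SSRS window |

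**Length of the uncovered interval**

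- Treatment Period: 52 weeks × 7 = 364 days.
- If Day 1 is the dosing day: 2 − 1 = 1 day to 4 − 1 = 3 days. As a share: 1/364 = 0.3% to 3/364 = 0.8%.
- If the visit is counted as 2 to 4 days after randomization (the MRI anchor): 2 to 4 days, less up to 6 hours between randomization and first dose. The upper end is 4/364 = 1.1%.
- Across about 120 subjects: 120 × 1 = 120 to 120 × 3 = 360 subject-days on the first reading, and at most 120 × 4 = 480 on the second.

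**Status of the first column**

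SAP 9.1 defines the safety baseline as the last observation before first dose. The first C-SSRS described comes after first dose, so it does not meet that definition by its date of administration. SAP 8.1 allows Day 2-4 to serve as baseline for some efficacy endpoints, but SAP 9.1 has no such provision for safety. The column's status therefore rests on its label, and the label names an assessment that the section does not describe.

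**What the adverse event route covers**

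Protocol 6.1 collects adverse events from study drug administration, whether solicited or spontaneous. SAP 9.2.1 treats any event with onset on or after the first dose date as treatment-emergent, and SAP 9.2.2 and 9.2.4 summarize these events, including serious events and deaths. This window spans the whole gap. It does not, however, require the 5 ideation and 6 behaviour questions of the C-SSRS to be asked about those days.

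**The case against.** A reader might infer that suicidal ideation or behaviour just after the first infusion is counted nowhere, or is certain to be missed as an on-treatment event. The documents do not support that. An event reported as an adverse event on Day 2 is treatment-emergent and is tabulated. One mentioned on the Day 2-4 form would also appear in the listing of affirmative responses, although under the wrong heading.

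There are three further points on the other side.

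- Recall instructions belong to data collection. The Activity Schedule (Protocol Appendix D) and Operations Manual (Appendix F) were not available for this review, and their absence is not a fault in the plan. The SAP sentence is loosely worded, and 9.5.2 does not define study entry or last visit. If the form actually used at Day 2-4, or the next one, reaches back to first dose, there is no gap in the data. This stands as a real uncertainty. It does not rescue the SAP text, which states two rules that leave the interval out.
- The phrase about the entire study duration in Protocol 3.4 closes a list of evaluations. It does not promise unbroken C-SSRS recall. This also stands: the phrase shows the intended scope of safety monitoring as a whole, and the finding does not depend on it.
- The C-SSRS output is descriptive, and Protocol 7.4 rules out hypothesis testing for safety. No estimate or decision rule changes. This limits the importance of the point, not its accuracy.

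**Conclusion.** The point holds in a limited form. On the plain wording of SAP 9.5.2, first dose to the Day 2-4 visit lies outside every C-SSRS recall window. The interval is about 1 to 3 days per subject, or up to about 4 days on the randomization anchor. Events in it would be missing from the C-SSRS tables or mixed with pre-study history. The loss is one of structured elicitation and correct classification within the C-SSRS, with adverse event reporting as a back-up.

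This rests on three assumptions: that study entry means a time no later than first dose, that the last visit before the next C-SSRS is the Day 2-4 visit, and that the Operations Manual does not set a different recall. The documents give no event rate, so no expected count can be calculated. With so short an interval few events are expected, and the point is minor.

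**What to change.** Amend SAP 9.5.2 as follows:

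1. Define study entry.
2. Have the Day 2-4 administration record history before study entry and, separately, experience since first dose. Alternatively, start the recall of the first later form at first dose.
3. Tabulate the since-first-dose answers as post-baseline.
4. Rename the first summary column as pre-study history (collected Day 2-4) in place of the screening label.
5. Check that the Operations Manual instruction agrees. If it already reaches back to first dose, one sentence in the SAP saying so settles the recall question.

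The cost is one added recall instruction at an existing visit, with matching wording in the SAP and, if needed, the Operations Manual. No new visit or instrument is required. If the data have already been collected, the missing recall cannot be recovered; correct the label and state the recall gap in the study report.
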